3.5 Outline of Study

This will be a multi-site, prospective, randomized, parallel crossover, double-masked study comparing 4 contact lenses. The expected duration of subject participation in the study is approximately 20 days, with 3 scheduled visits. The study is expected to be completed in approximately 7 weeks.

4 TREATMENTS ADMINISTERED

This is a 3-arm, parallel, crossover group study design. In each arm, the test lens will be evaluated compared to 1 of 3 chosen control lenses. Subjects will be randomized to 1 of the 6 lens sequences, as described below:

Sequence 1: DD T2 \rightarrow Oasys 1-Day

Sequence 2: Oasys 1-Day \rightarrow DD T2

Sequence 3: DD T2 \rightarrow MyDay

Sequence 4: MyDay \rightarrow DD T2

Sequence 5: DD T2 \rightarrow Moist

Sequence 6: Moist \rightarrow DD T2

Document: TDOC-0054506 Version: 1.0; CURRENT; Most-Recent; Effective

Status: Effective Page 13 of 38

4.1 Identity of Study Treatments

Table 4-1 Description of Test and Control Products

Day MyDay Moist 1 A stenfilcon A etafilcon A 54% 58% 8.4 8.5 14.2 14.2
A stenfilcon A etafilcon A 54% 58% 8.4 8.5
54% 58% 8.4 8.5
8.4 8.5
14.2
00 D -1.00 to -6.00 D -1.00 to -6.00 D (0.25 D steps) (0.25 D steps)
Blister foil pack Foil label includes at a minimum: In material name and/or identifier For base curve Inve diameter For packing solution For power For content statement For content statement For information ation For or information For origin For

Document: TDOC-0054506 Version: 1.0; CURRENT; Most-Recent; Effective

Status: Effective Page 14 of 38

	power per box, identified with the following at a minimum: - a color coded label stating the protocol number - material identifier - power	identified with the following at a minimum: - a color coded label stating the protocol number - material name or	the following at a minimum: - a color coded label stating the protocol number - material name or identifier - power	the following at a minimum: - a color coded label stating the protocol number - material name or identifier - power
	 an investigationa l use only statement tracking number Lenses should be stored at room temperature. 	identifier - power - an investigatio nal use only statement - tracking number • Lenses should be stored at room temperature.	 an investigatio nal use only statement - tracking number Lenses should be stored at room temperature. 	 an investigatio nal use only statement tracking number Lenses should be stored at room temperature.
Usage	Replacement p	vear al, parallel crossover eriod: Daily Dispos east 8 hours per day t duration.		week over the

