4.2 Accountability Procedures

Upon receipt of the study lenses, the Investigator or delegate will conduct an inventory. Designated study staff will provide the study lenses to the subjects in accordance with their randomization schedule. Throughout the study, the Investigator or delegate must maintain records of study treatment dispensation and collection for each subject. This record must be made available to the study monitor for the purposes of verifying the accounting of clinical supplies. Any discrepancies and/or deficiencies between the observed disposition and the written account must be recorded along with an explanation.

It is the Investigator's responsibility to ensure that:

All study products are accounted for and not used in any unauthorized manner

Document: TDOC-0054506 Version: 1.0; CURRENT; Most-Recent; Effective

Status: Effective Page 15 of 38

All used foils and unused supplies are returned by each subject

- All unused products are available for return to the Study Sponsor, as directed
- Any study lenses associated with a device deficiency or with any product-related adverse event [ie, ADE or SADE] are returned to the Study Sponsor for investigation. Refer to Section 7.3 of this protocol for additional information on the reporting of device deficiencies and AEs and the return of study products associated with these events.

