5 STUDY PROCEDURES AND ASSESSMENTS

5.1 Visits and Examinations

5.1.1 Visit 1 (Day 1) – Baseline/Dispense Lens 1

1	Explain the purpose and nature of the study, and have the subject read, sign, and date
	the IRB-approved informed consent document. Additionally, have the individual
	obtaining consent from the subject and a witness, if applicable, sign and date the
	informed consent document. Provide a photocopy of the signed document to the
	subject and place the original signed document in the subject's chart. After signing
	the ICF, a subject will be assigned a subject number by the EDC system. A signed
	informed consent document defines the point of enrollment.
2	Obtain demographic information and medical history, including information on all
	medications used within the past 30 days. Include herbal therapies, vitamins, and all
	over-the-counter as well as prescription medications.
3	
4	Perform Snellen VA with habitual correction.
	OD, OS, distance only, contact lenses
	Over-refraction (only needed if VA is reduced)
	Record habitual lens information (brand, power).
5	
6	

[figure not shown]
Document: TDOC-0054506 Version: 1.0; CURRENT; Most-Recent; Effective

Status: Effective Page 16 of 38

7	Perform slit-lamp biomicroscopy (without contact lenses) to evaluate the following:	
	Limbal hyperemia	
	Bulbar hyperemia	
	Corneal staining	
	Conjunctival staining	
	Palpebral conjunctival observations	
	Corneal epithelial edema	
	Corneal stromal edema	
	Corneal vascularization	
	Conjunctival compression/indention	
	• Chemosis	
	Corneal infiltrates	
	Other findings	
8		
9	Review inclusion/exclusion criteria to determine if the subject qualifies to be	
	randomized into the study. If subject qualifies, request randomization. If subject does	
	not qualify, exit the subject from the study as a screen failure.	
10	Based upon the randomized treatment sequence assignment, have the subject insert	
	the appropriate study lenses.	
	Keep all lidding foils of lenses used during lens fit process for study lens	
	accountability.	
11	Follow procedures to maintain masking.	
11		
12	Evaluate the study lenses by performing the following:	
12	Snellen VA with study lenses (OD and OS, at distance)*	
	Over-refraction if necessary to determine the best contact lens-corrected VA	
	and final study lens power(s)	
	*VA w/study lenses must be 20/40 OU or better for subject to leave the office	

Document: TDOC-0054506 Version: 1.0; CURRENT; Most-Recent; Effective

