6.4.1 Primary Effectiveness

The primary objective of this study is to evaluate the overall performance of DD T2 lenses when compared to Oasys 1-Day, MyDay and 1-Day Acuvue Moist. The primary endpoint is the subjective rating on overall quality of vision, collected binocularly on a scale of 1 (Poor) to 10 (Excellent).

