8 CONFIDENTIALITY, BIAS, AND MASKING

8.1 Subject Confidentiality and Methods Used to Minimize Bias

The Investigator must ensure that the subject's anonymity is maintained throughout the course of the study. In particular, the Investigator must keep an enrollment log with confidential identifying information that corresponds to the subject numbers and initials of each study participant. At the end of the clinical study, the Sponsor will collect a copy of the enrollment log without any identifying subject information. All documents submitted to the Sponsor will identify the subjects exclusively by number and demographic information. No other personally identifying information should be transmitted to the Sponsor.

This study is double-masked with subjects randomized to use both DD T2 and the assigned control product (in a randomized sequence) for the duration of the treatment period. The Investigator and Sponsor personnel (other than site monitors, lead clinical site manager, person responsible for generating the randomization schedule, and unmasked clinical data managers) involved in reporting, obtaining, and/or reviewing the clinical evaluations will be masked to the identity of the contact lens being administered. This level of masking will be maintained throughout the conduct of the study. Unmasking will occur only after all planned study data have been validated, and the database locked. Masked study personnel must avoid seeking information that may compromise masking. Unmasked study personnel must not disseminate information that is potentially unmasking to any masked personnel. The **masked** and **unmasked** site personnel must coordinate all study activities as necessary to protect masking and minimize bias during the trial.

Document: TDOC-0054506 Version: 1.0; CURRENT; Most-Recent; Effective

Status: Effective Page 35 of 38

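### Does the labelling in Table 4-1, together with the list of masked parties in protocol 8.1, leave the subject's own primary rating unmasked?

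*Protocol*

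**What the plan says.** **Masking.** Protocol 3.5 and 8.1, and SAP 1.2 (Table 1-1) and 1.4, all call the study double-masked. Protocol 8.1 then says that the Investigator and Sponsor personnel, apart from some listed roles, "will be masked to the identity of the contact lens being administered". Subjects appear in that paragraph as randomised to wear both lenses, not as a masked party. SAP 1.4 is one sentence and names nobody.

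**Endpoint.** Protocol 6.4.1 and SAP 4.1 make the subject's binocular 1-10 rating of overall quality of vision the primary endpoint. It is collected by questionnaire at Visits 2 and 3.

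**Labels.** In protocol Table 4-1 the foil is to carry at least "material name and/or identifier", among other items. The control boxes carry "a color coded label stating the protocol number - material name or identifier - power". The first column, which appears to be the test lens, has "a color coded label stating the protocol number - material identifier - power".

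**Handling.** Protocol 5.1.1 says "Based upon the randomized treatment sequence assignment, have the subject insert" the study lenses, and the next readable step is "Follow procedures to maintain masking". Protocol 4.2 makes the Investigator responsible for seeing that "All used foils and unused supplies are returned by each subject".

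**The concern.** The person who produces the primary endpoint is the person whose masking matters most, and that person is missing from the one sentence that lists the masked parties. The rule in 8.1 against passing on unmasking information likewise protects masked personnel and does not mention the subject. The label table leaves room for a material name on packs that the subject opens.

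Every subject wears the test lens and one marketed control. A subject who could tell from the print which was which might rate on expectation. That shift would attach to the lens, so randomising the order would not balance it out. The primary result is means and category counts, and the shift would pass straight into them.

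**Working it through.** The plan has no figure to reproduce: protocol 6.4.1.1 and SAP 4.2 state no hypotheses, so there is no power, margin or error rate. The check is one line of algebra followed by a comparison of passages.

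**1. Would the crossover remove an expectation effect?** Let T and C be the mean ratings of test and control, p1 and p2 the period effects, and b the shift in control ratings caused by recognising the lens.

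- Test first: test minus control = (T + p1) − (C + b + p2) = T − C − b + (p1 − p2).
- Control first: test minus control = (T + p2) − (C + b + p1) = T − C − b − (p1 − p2).
- Average of the two sequences: T − C − b.

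The period effects cancel and b remains. The mechanism is sound if b is not zero. Nothing in either document gives a value for b.

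**2. Does the plan leave the subject unmasked?** The synopsis design list has separate entries for masking the trial subject alone, masking the Investigator alone, double-masked and open-label. Set beside the two single-masked entries, double-masked means both parties. On that reading, the sentence in 8.1 says which staff are masked and which are exempt. It is not a complete list of everyone masked.

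**3. Does the label rule disclose the lens?** The foil wording is and/or, and the control-box wording is or. An identifier alone satisfies both. The lists are minimum contents, so the first column does not say that the test box carries an identifier and nothing else. Nor does the table say that any name is printed on a control box.

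**4. Would a printed name lead to a biased rating?** It would have to tell the subject which lens was the marketed one.
- The item is a material name, such as senofilcon A, not a brand.
- Exclusion criterion 14 removes current wearers of all three controls.
- The readable label lists put an investigational-use statement on all four boxes.
- Noticing that two foils differ is not the same as knowing which is the test lens.

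**5. Is concealment left without a procedure?** A masking step follows insertion in 5.1.1. Section 8.1 provides for separate masked and unmasked site personnel. The steps near lens insertion are partly blank in the public text (the second line numbered 11 in 5.1.1, and step 9 in 5.1.2). A manual of procedures accompanies the protocol (7.3) but is not among the documents. Blank or unsupplied text cannot be counted as absent from the plan.

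**The case for a change.** The strongest reply is that implication is not enough for the outcome assessor. Section 8.1 reads continuously where it lists the masked parties, so redaction does not explain the omission. The label lists set a floor and forbid nothing, and the one visible masking instruction has no content. Former wearers of the controls are not excluded by criterion 14 and might recognise a material name. The absence of hypothesis tests removes concern about type I error but does nothing about bias, and protocol 3.1 says the data will inform product development.

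Most of this is accurate. It stands as an observation that the readable text does not name the subject in 8.1 and does not say how lens identity is kept from the subject. It does not show that following the plan, including its masking step, gives a wrong result.

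The available remedies gain little:
- Naming the subject in 8.1 and SAP 1.4 repeats what double-masked already means and alters no procedure, table or figure.
- Requiring a code on the boxes leaves open what the foils may carry.
- Coding the manufacturers' own foils may go beyond the sponsor labels described for the boxes. It would still leave base curve among the foil contents, and Table 4-1 gives 8.4 for MyDay and 8.5 for Moist, so foils could differ in print anyway.
- Describing the study as masked for Investigator and Sponsor only would be right if subjects were known to be unmasked, and nothing shows that.

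**Conclusion.** No change to the plan follows. The omission in 8.1 is missing detail that a reader fills correctly from the term double-masked and the synopsis design list. The wording in Table 4-1 is permissive and can be met without disclosing the lens.

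The size of any bias is unknown. It would equal b, the shift in ratings from recognising a lens, and the documents neither give b nor show that it differs from zero. No success criterion or test depends on it: the SAP executive summary says that success criteria do not apply.

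This rests on three assumptions: that double-masked has its usual meaning, that site staff carry out the masking step as instructed, and that the unread steps or the manual do not contradict it. Table 4-1 reached this review with broken columns, so no claim is made about differences between test and control foils. Evidence that subjects were given packs with recognisable names would reopen the point, as a matter of conduct and of how the masking is reported.

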4.2 Accountability Procedures

Upon receipt of the study lenses, the Investigator or delegate will conduct an inventory. Designated study staff will provide the study lenses to the subjects in accordance with their randomization schedule. Throughout the study, the Investigator or delegate must maintain records of study treatment dispensation and collection for each subject. This record must be made available to the study monitor for the purposes of verifying the accounting of clinical supplies. Any discrepancies and/or deficiencies between the observed disposition and the written account must be recorded along with an explanation.

It is the Investigator's responsibility to ensure that:

All study products are accounted for and not used in any unauthorized manner

Document: TDOC-0054506 Version: 1.0; CURRENT; Most-Recent; Effective

Status: Effective Page 15 of 38

All used foils and unused supplies are returned by each subject

- All unused products are available for return to the Study Sponsor, as directed
- Any study lenses associated with a device deficiency or with any product-related adverse event [ie, ADE or SADE] are returned to the Study Sponsor for investigation. Refer to Section 7.3 of this protocol for additional information on the reporting of device deficiencies and AEs and the return of study products associated with these events.

5 STUDY PROCEDURES AND ASSESSMENTS

5.1 Visits and Examinations

5.1.1 Visit 1 (Day 1) – Baseline/Dispense Lens 1

1	Explain the purpose and nature of the study, and have the subject read, sign, and date
	the IRB-approved informed consent document. Additionally, have the individual
	obtaining consent from the subject and a witness, if applicable, sign and date the
	informed consent document. Provide a photocopy of the signed document to the
	subject and place the original signed document in the subject's chart. After signing
	the ICF, a subject will be assigned a subject number by the EDC system. A signed
	informed consent document defines the point of enrollment.
2	Obtain demographic information and medical history, including information on all
	medications used within the past 30 days. Include herbal therapies, vitamins, and all
	over-the-counter as well as prescription medications.
3	
4	Perform Snellen VA with habitual correction.
	OD, OS, distance only, contact lenses
	Over-refraction (only needed if VA is reduced)
	Record habitual lens information (brand, power).
5	
6	

[figure not shown]
Document: TDOC-0054506 Version: 1.0; CURRENT; Most-Recent; Effective

Status: Effective Page 16 of 38

7	Perform slit-lamp biomicroscopy (without contact lenses) to evaluate the following:	
	Limbal hyperemia	
	Bulbar hyperemia	
	Corneal staining	
	Conjunctival staining	
	Palpebral conjunctival observations	
	Corneal epithelial edema	
	Corneal stromal edema	
	Corneal vascularization	
	Conjunctival compression/indention	
	• Chemosis	
	Corneal infiltrates	
	Other findings	
8		
9	Review inclusion/exclusion criteria to determine if the subject qualifies to be	
	randomized into the study. If subject qualifies, request randomization. If subject does	
	not qualify, exit the subject from the study as a screen failure.	
10	Based upon the randomized treatment sequence assignment, have the subject insert	
	the appropriate study lenses.	
	Keep all lidding foils of lenses used during lens fit process for study lens	
	accountability.	
11	Follow procedures to maintain masking.	
11		
12	Evaluate the study lenses by performing the following:	
12	Snellen VA with study lenses (OD and OS, at distance)*	
	Over-refraction if necessary to determine the best contact lens-corrected VA	
	and final study lens power(s)	
	*VA w/study lenses must be 20/40 OU or better for subject to leave the office	

Document: TDOC-0054506 Version: 1.0; CURRENT; Most-Recent; Effective

Status: Effective Page 17 of 38

5.1.2 Visit 2, Week 1 [Day 8 (-1/+2 Days)] – Follow-Up Lens 1/Dispense Lens 2

1	Obtain information on any changes in medical health and/or the use of concomitant medications.
2	Record any device deficiencies or AEs including those associated with changes in concomitant medication dosing, which are observed or reported since the previous visit(s).
3	Review subject compliance with lens wear and adjunct product usage.
4	Administer Subjective Questionnaire to assess: Subjective overall quality of vision, OU Subjective overall quality of vision, OU

[figure not shown]
Document: TDOC-0054506 Version: 1.0; CURRENT; Most-Recent; Effective

Status: Effective Page 18 of 38

Status.	tus. Effective			
5	Evaluate the study lenses by performing the following:			
	Snellen VA with study lenses (OD and OS, at distance)			
6				
7	Perform slit-lamp biomicroscopy (without contact lenses) to evaluate the following:			
	Limbal hyperemia			
	Bulbar hyperemia			
	Corneal staining			
	Conjunctival staining			
	Palpebral conjunctival observations			
	Corneal epithelial edema			
	Corneal stromal edema			
	Corneal vascularization			
	Conjunctival compression/indention			
	• Chemosis			
	Corneal infiltrates			
	Other findings			
8	Based upon the randomized treatment sequence assignment, have the subject insert			
	the Lens 2 study lenses to be evaluated. Note: Keep all lidding foils of lenses used during lens fit process for study lens			
	accountability.			
9				
10	Evaluate the study lenses by performing the following:			
	Snellen VA with study lenses (OD and OS, at distance)*			
	Over-refraction if necessary to determine the best contact lens-corrected VA			
	and final study lens power(s)			
	* VA w/study lenses must be 20/40 OU or better for subject to leave the office			

Document: TDOC-0054506 Version: 1.0; CURRENT; Most-Recent; Effective

Status: Effective Page 19 of 38

5.1.3 Visit 3, Week 2 [Day 8 (-1/+2 Days)] – Follow-Up Lens 2/Exit

1	Obtain information on any changes in medical health and/or the use of concomitant
	medications.
2	Record any device deficiencies or AEs including those associated with changes in
	concomitant medication dosing, which are observed or reported since the previous
	visit(s).
3	Review subject compliance with lens wear and adjunct product usage.
4	Administer Subjective Questionnaire to assess:
	•
	•
	•
	•
	Subjective overall quality of vision, OU
	•
	•
	•

Document: TDOC-0054506 Version: 1.0; CURRENT; Most-Recent; Effective

Status: Effective Page 20 of 38

5	Evaluate the study lenses by performing the following:
	Snellen VA with study lenses (OD and OS, at distance)
6	
7	Perform slit-lamp biomicroscopy (without contact lenses) to evaluate the following:
	Limbal hyperemia
	Bulbar hyperemia
	Corneal staining
	Conjunctival staining
	Palpebral conjunctival observations
	Corneal epithelial edema
	Corneal stromal edema
	Corneal vascularization
	Conjunctival compression/indention
	Chemosis
	Corneal infiltrates
	Other findings
8	Assess and record any AEs and device deficiencies reported or observed during the
	study visit.
	Note: AEs and device deficiencies must be recorded for all enrolled subjects from
	the time of signature of informed consent regardless of their enrollment status (screen failure or randomized).
9	Perform Snellen VA with habitual correction.
9	OD, OS, distance only, contact lenses
	Note: If this VA with habitual correction shows a decrease of 2 lines or more versus
	Visit 1 baseline VA with habitual correction, then BCVA with MR is required to
	confirm a potential loss in VA for AE reporting requirements (see Section 7).
10	Exit the subject from the study.

Document: TDOC-0054506 Version: 1.0; CURRENT; Most-Recent; Effective

Status: Effective Page 21 of 38

5.2 Unscheduled Visits

Any visit that occurs between regularly scheduled visits is an Unscheduled Visit. If a subject requires an Unscheduled Visit, he/she must be advised to return to the office wearing the study lenses, if at all possible (unless he/she is experiencing a sign or symptom [as indicated in Section 3.3 Risks and Benefits]). During all unscheduled visits, the Investigator must conduct the following procedures:

- Collect AE and device deficiency information
- Assess and record changes in medical condition or concomitant medication
- Assess and record VAs
- Perform biomicroscopy (assessments with or without lenses, as possible)

In addition, all procedures for Visit 3 (Follow-up Lens 2/Exit) should be completed (as possible). The Investigator may perform additional procedures for proper diagnosis and treatment of the subject. The Investigator must document this information in the subject's case history source documents.

If during an Unscheduled Visit the subject is discontinuing the study lenses or discontinuing from the study, the Investigator must conduct Exit procedures according to Table 1-1: Schedule of Study Procedures and Assessments, as possible.

